3. STUDY DESIGN

The main objective of this single blind study is to evaluate wearable devices and Observer Reported Itch Assessment in children to assess reduction of itch and night-time scratch in response to Crisaborole treatment vs. vehicle treatment in children with AD. Participants, age 3 months to ≤ 11 years with symptomatic mild to moderate AD, along with their primary caregivers will be recruited and assessed by observed scratch behavior captured from accelerometry/actigraphy.

Approximately 270 children, age 3 months to ≤ 11 years, and their primary caregiver as participants, for a total of 540 participants (270 pairs), will be randomized in 1:1 ratio to either Crisaborole (2% BID) or vehicle treatment and will be followed for 2 weeks, with an objective of approximately 50% of recruited child participants being ages 5 years old or younger. For this study, we will employ a simple randomization procedure. Participants will be randomly assigned (1:1) using computerized random numbers to receive either crisaborole or the vehicle. The participants will be asked to apply a thin even-layer of Crisaborole 2% or vehicle twice daily (excluding mouth, eyes, and vagina, per label), to all locations with active lesions and record location and time of application on the daily dosing form (as identified on the Dosing Record Sheet, breastfeeding women will be instructed to use the provided gloves when applying crisabrole/vehicle). The study will be comprised of an initial screening/baseline visit for children participants who have an existing diagnosis of symptomatic AD, screened and enrolled in the study along with their primary caregivers after signing an informed consent (or parents/guardians and assent when appropriate). Upon enrollment child participants and caregiver participants will complete a one week acclimation and training phase, where the children will not be on medication, for wearing accelerometry/actigraphy and performing observer-reported outcome assessments (caregivers for participants) and self-reported outcome assessments (caregivers). After the one week acclimation and training phase, the child participants will be on a Crisaborole or vehicle treatment for two consecutive weeks. During those 2 weeks, the children, 3 months up to <2 years will wear one actigraphy or one accelerometry device on each wrist and one actigraphy or one accelerometry device on each ankle (optional for those who have active AD on location of device placement, with a minimum of at least one wrist device needed for enrollment). Children 2 years to ≤ 11 years will wear one actigraphy or one accelerometry device on each wrist (optional for those who have active AD on location of device placement, with a minimum of at least one wrist device needed for enrollment). The primary caregiver (parents/guardians) will also wear one accelerometer device on each wrist and complete daily assessments related to scratching, sleeping habits, pain, AD severity, quality of life, and device comfort questionnaires (parent/guardian will complete as appropriate). The participants will be asked to return to the laboratory

on days 1, 2, 8, and 15 for assessments and biomarker assessment. At the completion of the study, Day 15 (± 3 day) participants (and primary caregiver) will return the devices, and will complete additional questionnaires. Participants may come in for an unscheduled visit as needed (i.e., to replace compound, etc.)

The goal of this study is to more fully evaluate the rapid onset of night-time itch and scratch relief following treatment with Crisaborole in comparison to vehicle treatment in children with AD. Moreover, this study will assess the QoL and sleep within the associated caregivers.

4. PARTICIPANT SELECTION

This protocol can fulfill its objectives only if appropriate participants are enrolled. Prior to undergoing any study procedures, a participant must meet this protocol's Inclusion/Exclusion criteria.

4.1. Inclusion Criteria

Both child and caregiver participants must meet all of the following inclusion criteria to be eligible for enrollment into the study:

Children (3 months to ≤ 11 years)

1. Male or female participants aged between ≥ 3 months of age and ≤ 11 years of age at Day -7.
2. Written informed consent from participant/parent(s)/guardian(s).
3. Native English or demonstrated fluency in English (as age appropriate).
4. Participants and parent(s)/guardian(s) are willing and able to comply with study instructions, study visits, procedures, and device placement (devices will be optional for those who have active AD on location of device placement, with a minimum of at least one wrist device needed for enrollment).
5. Have a clinical diagnosis of AD according to the criteria of Hanifin and Rajka.
6. Have AD involvement $\geq 5\%$ Treatable % Body Surface Area (BSA) excluding the scalp and less than 40% BSA.
7. Have an ISGA score of Mild (2) or Moderate (3) at the baseline visit.
8. Have an EASI total score of ≥ 3 at Day -7.
9. Have a minimum Observer Reported Itch Assessment score of 2 at Day -7 (ages 3 months - ≤ 5 years only) or a minimum Patient Reported Itch Severity Scale score of 2 (ages 6 years - ≤ 11 years old) at Day -7.
10. Participant/parent(s)/guardian(s) agrees to refrain from applying diaper rash creams, lotions, ointments, powders, etc. where AD lesions are present, unless AD lesions are present where crisaborole cannot be applied (face within 1 or 2 fingers away from the mouth and hands/fingers).
11. Participants must agree to refrain from applying crisaborole/vehicle to AD lesions on the fingers or hands or within 1 or 2 fingers away from the the mouth to prevent inadvertent ingestion of ointment.

Adult Caregiver

1. Primary caregiver of the child participant, between ≥ 18 years of age and ≤ 75 years of age.
2. Able to understand and cooperate with study procedures and give informed consent.
3. Native English or demonstrated fluency in English.
4. Evidence of a personally signed and dated informed consent document indicating that the participant has been informed of all pertinent aspects of the study.
5. ISGA score of 0 or 1 of AD at the baseline visit, and no reported diagnosis of Atopic Dermatitis.
6. WRAT-4 Word Reading Subtest equivalent to 8th grade reading level or greater.

4.2. Exclusion Criteria

Participants (either child or caregiver) presenting with any of the following will not be included in the study:

Children (3 months to \leq 11 years)

1. Has any clinically significant medical disorder, condition, disease (including active or potentially recurrent non-AD dermatological conditions and known genetic dermatological conditions that overlap with AD, such as Netherton syndrome) or clinically significant finding at baseline that precludes participant's participation in study activities.
2. Participants who are on systemic corticosteroids or immunosuppressive agents within 28 days of Day -7 (V01).
3. Participants who are on topical AD treatment such as low-to-high-potency corticosteroids, TCIs, antihistamines, antibiotics, sodium hypochlorite-based products, antibacterial soaps, bleach baths, diaper rash creams, lotions, ointments, powders, light therapy, and use of bland emollients on or overlapping with treatable AD-involved areas within 7 days of Day -7 (V01), unless AD lesions are present where crisaborole cannot be applied (face within 1 or 2 fingers away from the mouth and hands/fingers).
4. Participants who are or have been on crisaborole treatment regimen in the past.
5. Allergy to polyurethane resin (strap/wristband component), skin nickel allergy, silicone, and/or adhesives.
6. Has documented non-AD related insomnia, sleep apnea or other sleep-related disorders (e.g., narcolepsy, restless legs syndrome, circadian rhythm disorder).
7. Participant has a known lack of efficacy to any component of crisaborole.
8. Participant scores <20 on the Childhood Asthma Control Test (ages 4- \leq 11) indicating poorly controlled asthma.
9. If participant has a history of angioedema or anaphylaxis.
10. Has a significant active systemic or localized infection, including actively infected AD.
11. Has any planned surgical or medical procedure that would overlap with study participation.
12. Participants with cardiac pacemakers, electronic pumps or any other implanted medical devices.
13. Participants who are unable to wear at least one wrist device (one accelerometry device on at least one wrist).

Adult Caregiver

1. Has any clinically significant medical disorder, condition, disease or clinically significant finding at baseline that precludes Caregivers participation in study activities (e.g., sleep apnea, narcolepsy, etc.)
2. History of regular alcohol consumption exceeding 7 drinks/week for females or 14 drinks/week for males (1 drink = 5 ounces (150 mL) wine, 12 ounces (360 mL) of beer, or 1.5 ounces (45 mL) of hard liquor) within 6 months of baseline as disclosed by participant during evaluation.^{*}
3. Current shift worker or travel across more than two time zones in the past 2 weeks, and/or during the study period.
4. Has any planned surgical or medical procedure that would overlap with study participation.
5. Participants who are investigational site staff members directly involved in the conduct of the study and their family members, site staff members otherwise supervised by the investigator, or participants who are BU/BMC employees directly involved in the conduct of the study.
6. Allergy to polyurethane resin (strap/wristband component), skin nickel allergy, silicone, and/or adhesives.
7. A female who is pregnant.[†]
8. The primary caregiver or share the same domicile of another child who has previously been or is currently enrolled in the study.

* One of our secondary objectives is to evaluate sleep in primary caregivers. It is noted in the literature that alcohol use and abuse has significant effect on sleep as it can cause insomnia, excessive daytime sleepiness, and changes in sleep homeostasis/architecture (Colrain, Burlington, & Baker, 2009; Hu, et al., 2020). Thus to ensure that we can effectively capture sleep in primary caregivers of children with AD (who experience sleep disturbances), we will be excluding caregivers who have sleep disorders, are shiftworkers or have traveled more than two time zones in the past 2 weeks and/or during the study period, as well as those who have a history of regular alcohol consumption exceeding 7 drinks/week for females or 14 drinks/week for males.

[†]There is currently no data available regarding associated risks of pregnant women applying crisaborole to their child. Thus, pregnant women are excluded from the study as a precautionary measure. Furthermore, per the crisaborole FDA label, for the use of crisaborole on pregnant women "There is no available data with EUCRISA in pregnant women to inform the drug-associated risk for major birth defects and miscarriage." Since this data is not available, the risks of including a pregnant woman do not outweigh the benefits of the study. Women of child-bearing potential will be pregnancy tested using a standard drug-store urine test at the Laboratory for Human Neurobiology. If the participant suspects that they are pregnant, or test results indicate that they may be pregnant, they will be asked to follow up with their doctor and they will not be included in the study.

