Mitigation of risk associated with tape stripping: Tape stripplings will only be conducted three times with a minimum of 3 days between each tape stripping. If the participant experiences discomfort, adjacent sites to previous stripping area will be used.

Possible risk associated with crisaborole: Possible risks associated with crisaborole include application site pain or burning/stinging sensation (lasting one to two days) and/or hypersensitivity reaction and/or development of a skin allergy and/or severe pruritis and/or swelling and/or erythema. Less common risks (<1%) include contact urticaria (hives - a skin reaction that results in red, itchy welts). AD by nature is a disease that has recurrent flares on active treatment or without active treatment. Therefore, participants on crisaborole or vehicle could experience worsening of their natural course of disease.

Mitigation of risk associated with crisaborole: If the participant develops a hypersensitivity reaction, severe pruritis, swelling, or erythema, (and/or development of skin allergy (e.g. hives)), dosing will be discontinued and the site will be contacted, and the participant should seek medical attention as needed. If minor application site pain or burning/stinging sensation is reported, and participant is uncomfortable with continuation, the principal investigator may allow the participant to continue in the study with dosing discontinued, or participant will be withdrawn. If signs and symptoms of hypersensitivity occur, discontinue EUCRISA immediately and initiate appropriate therapy. **Hypersensitivity Reactions** Advise patients to discontinue EUCRISA and seek medical attention immediately if signs or symptoms of hypersensitivity occur [see *Warnings and Precautions (5.1) from label*]. **Administration Instructions** Advise patients or caregivers that EUCRISA is for external use only and is not for ophthalmic, oral, or intravaginal use. All participants may withdraw from the study at any time, including if they experience worsening of symptoms.

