Possible Risk Associated with vehicle treatment: Possible risks associated with vehicle include application site pain or burning/stinging sensation, severe pruritis (itching), swelling, redness and/or hypersensitivity reaction (an exaggerated immune response which may cause skin discomfort) and/or development of a skin allergy. Possible risks associated with vehicle treatment where vehicle contains the excipients of crisaborole ointment, and the base of crisaborole ointment has no difference in appearance, texture, color, or odor to crisaborole ointment, 2% and as such no specific risks identified other than hypersensitivity reaction and/or development of skin allergy. No additional risks are known with respect to vehicle treatment as it provides white petrolatum as the main excipient and base of crisaborole ointment, 2%, which was selected for its emollient properties and favorable tolerability profile, where the importance of an emollient effect is highlighted by the use of emollients in basic skin care for patients with AD, to aid in restoration of barrier function

Mitigation of Risk Associated with vehicle treatment: If the participant develops a hypersensitivity reaction, severe pruritis (itching), swelling, redness (and/or development of skin allergy (e.g. hives)), dosing will be discontinued and the site will be contacted, and the participant should seek medical attention as needed. If minor application site pain or burning/stinging sensation is reported, and participant is uncomfortable with continuation, the principal investigator may allow the participant to continue in the study with dosing discontinued, or participant will be withdrawn. AD by nature is a

disease that has recurrent flares on active treatment or without active treatment. Therefore, participants on vehicle could experience worsening of their natural course of disease.

Participants may become bored/fatigued over the course of a testing session. The same considerations apply to the study visits.

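### Child exclusion 7 asks about lack of efficacy, and no child criterion expressly excludes a known allergy to the ointment base or excipients short of angioedema or anaphylaxis

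*Combined protocol and SAP*

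**What the plan says.** All eligibility text is in Section 4, and the child exclusions are in Section 4.2. Five of them bear on this point:

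- Exclusion 7: "Participant has a known lack of efficacy to any component of crisaborole".
- Exclusion 4: "Participants who are or have been on crisaborole treatment regimen in the past".
- Exclusion 5, the only child criterion that names allergy: "Allergy to polyurethane resin (strap/wristband component), skin nickel allergy, silicone, and/or adhesives".
- Exclusion 9: "If participant has a history of angioedema or anaphylaxis".
- Exclusion 1, a general clause on clinically significant disorders, which includes active or potentially recurrent skin conditions other than AD and ends with a "clinically significant finding at baseline that precludes participant's participation in study activities".

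The safety text is in Section 8. Section 8.2 puts hypersensitivity first in its list of risks to be monitored. For crisaborole, Section 8.4 lists application-site pain together with "hypersensitivity reaction and/or development of a skin allergy and/or severe pruritis and/or swelling and/or erythema". For vehicle it also lists hypersensitivity and skin allergy, and it states that the "vehicle contains the excipients of crisaborole ointment", with white petrolatum as the main one. Management begins once a reaction has occurred: "If signs and symptoms of hypersensitivity occur, discontinue EUCRISA immediately and initiate appropriate therapy". The vehicle paragraph likewise provides for dosing to be discontinued.

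**The concern.** The risk section and the eligibility list do not meet. Section 8.4 treats an allergic reaction to the study ointment as foreseeable in both arms. The one criterion about components of the product asks a different question, namely whether a component has failed to work. The authors did write an express allergy criterion for the devices a child wears, but none for the ointment that is applied twice daily for two weeks.

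The main issue is participant protection. A site that follows the list literally could enrol a child with a documented contact allergy to a base ingredient. Because both arms receive the base, allocation to vehicle would not spare that child the exposure. There is also a smaller measurement issue. The Observer Reported Itch Assessment (ORIA) is a primary endpoint, and severe itch is among the reactions Section 8.4 lists for each arm, so an avoidable reaction would feed into the outcome and into discontinuation.

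**Working it through.** The plan gives no figure on this point, so the check is a comparison of texts.

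**Step 1. Is there an allergy screen for the ointment?** I read all child inclusion criteria (Section 4.1) and exclusion criteria (Section 4.2). None names allergy or hypersensitivity to crisaborole, to the vehicle or to an excipient. The materials in exclusion 5 (polyurethane resin, nickel, silicone, adhesives) include no ointment ingredient that the documents state.

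**Step 2. What does exclusion 7 do as written?**
- *Applied to the active drug.* A child can be known not to respond only after using it, and exclusion 4 removes children with a past or current crisaborole regimen. Exclusion 7 therefore adds almost nobody. I say almost because a regimen need not cover every single exposure.
- *Applied to the excipients.* Taken literally, a child whose petrolatum emollient did not help would be excluded. That sits badly with exclusion 3, which handles bland emollients on treatable areas by a 7-day washout and so expects emollient users to enrol. The intended meaning is unclear.

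**Step 3. What gap is left after the other criteria?**

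| Child with a known reaction | Criterion that applies | Expressly excluded? |
|---|---|---|
| To crisaborole ointment, after a past regimen | 4 | Yes |
| With angioedema or anaphylaxis, any cause | 9 | Yes |
| To a device material named in the list | 5 | Yes |
| To the base or an excipient, without angioedema or anaphylaxis | 1, if the investigator judges that it precludes participation | No |

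Only the last row is open.

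**Step 4. Can it be sized?** Let p be the share of otherwise eligible children in the last row. The expected number is 270 × p, and the documents give no p. Purely as an assumed range, 0.5% gives 270 × 0.005 = 1.4 children and 2% gives 270 × 0.02 = 5.4. Nothing in the documents anchors that range. If p were instead the prevalence of any excipient allergy, the product would be too high, because criteria 1, 4 and 9 remove some of those children.

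**Step 5. Does it touch the sample size?** No. With SD 2.6, difference 1.0, two-sided 5% and 85% power (Section 9), n per arm = 2 × (1.960 + 1.036)² × 2.6² / 1.0² = 121.4, rounded up to 122, or 244 in total as stated. Power at 122 per arm is 85.2%. Allowing for 10% dropout, 244 / 0.90 = 271.1, against the stated approximate 270. No eligibility wording enters these formulas.

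**The case against.** The strongest case on the other side is that the list already does most of the work. Exclusion 4 removes most children who have reacted to crisaborole itself. Exclusion 9 covers angioedema as well as anaphylaxis, from any cause. A documented contact allergy fits naturally under the potentially recurrent skin conditions in exclusion 1, and ointment application is the central study activity. On study, staff check skin irritation at each visit, a 24-hour telephone line is available (Section 8.2), and Section 8.4 provides for stopping in both arms. Most of this stands. It narrows the gap to base or excipient allergy that is not expressly excluded. It does not close the gap, because exclusion 1 depends on judgement and does not name allergy, and the Section 8 measures act only after exposure.

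A reader might infer three stronger things that the documents do not support:

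- *That the efficacy wording is a slip for hypersensitivity.* The phrasing makes this plausible, but no section says so, and the point does not need it.
- *That all 270 children enter with no allergy enquiry.* Medical history, including AD treatment, is taken at the phone screen and again at V01 (Schedule of Activities; Section 5). Section 10.4 mentions a Phone Screening Questionnaire whose content is not reproduced. What it asks about allergy is unknown.
- *That the comparison is biased or underpowered.* Reactions to a shared base are expected equally in both arms. Even 5 of 270 is 1.9%, well inside the planned dropout of about 10%.

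**Conclusion.** The point holds in a limited form. Exclusion 7 is nearly redundant for the active drug and unclear for the excipients, and no child criterion expressly addresses known base or excipient allergy short of angioedema or anaphylaxis, although Section 8 names hypersensitivity as a risk and Section 8.4 does so for each arm. This is an omission and an unclear criterion rather than a direct contradiction, since risk and stopping text can coexist with an incomplete eligibility list. It is worth correcting for participant protection in children as young as 3 months. It does not threaten the validity of the trial: sample size, power, alpha and the between-arm comparison are unaffected. The number of children concerned cannot be derived from the documents and is probably small.

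The conclusion rests on two readings: that a past reaction to crisaborole ointment normally implies a past regimen caught by exclusion 4, and that exclusion 1 is applied at the investigator's discretion.

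**What to change.** Reconcile child exclusion 7 with Sections 8.2 and 8.4 so that the component criterion addresses the hypersensitivity risk those sections name, for the ointment and for its vehicle. Remove the lack-of-efficacy wording, or state what it is meant to exclude beyond exclusion 4. Confirm that the existing phone-screen and V01 medical history captures the information needed to apply the criterion, and add a question only if it does not.

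The cost is a one-line amendment with IRB approval, at most one screening question, and possibly a few more screen failures. No analysis or sample-size text needs to change.

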5. STUDY PROCEDURES

The study will consist of a screening/baseline (in- laboratory) visit on Day -7 (V01), an in- laboratory visit Day 1 (V02), an in- laboratory visit on Day 2 (V03) for tape-stripping, and Day 8 (V04) for an assessment of the severity of the AD and a final in- laboratory visit on Day 15 (V05) for an assessment of the AD, tape-stripping, completion of ObsROs and return devices. Throughout the study, the participants and caregivers will wear accelerometry/actigraphy devices continuously (optional for those who have active AD on location of device placement, with a minimum of at least one wrist device needed for enrollment; devices may be removed for short periods of time for such things as the purposes of bathing, etc.). Enrolled participants will be randomly assigned to each arm of the study. Participants may come in for an unscheduled visit as needed (i.e., to replace compound, etc.). All in-person study activities, including informed consent and pregnancy testing, will be completed at the Laboratory for Human Neurobiology, [name]. All activities performed in the laboratory are accomplished in private rooms. Primary caregivers will be provided with ample time and a privacy curtain to change into a gown during assessment for exclusion of Atopic Dermatitis, and primary caregivers will accompany children during all activities to ensure participant privacy. All at-home study activities will be completed in the participants' home.

Phone Screening - Day-28 to -7 (~15 minutes):

- Verbal consent (including assent where applicable)
- Assign Participant ID (a sequentially assigned numerical ID used to identify participant on all study documents and in the electronic data capture [EDC] system)
- Screening demographics, medical history including AD history/treatment (includes, race, ethnicity, and gender)
- Eligibility screening (review of inclusion and exclusion criteria)

Baseline Visit 1 (V01)/Day -7 (+/- 3) – In Laboratory (~2 hours):

- Written Informed consent (including assent when applicable)
- Participants are randomly assigned to one of the two arms of the study
- Screening demographics (includes race, ethnicity, gender, and significant medical

history/treatment)

- Pregnancy test for female caregivers of child-bearing potential
- Wide Range Achievement Test 4 (WRAT-4)
- Eligibility Screening (Inclusion/Exclusion criteria)
- Vital signs
- Height and weight
- Investigator's Static Global Assessment (ISGA) (scored by a dermatologist or a medically qualified individual who has been trained in the assessment; rater to be consistent throughout study)
- EASI assessment (scored by a dermatologist or a medically qualified individual who has been trained in the assessment; rater to be consistent throughout study)
- Calculate % body surface area (BSA) affected with AD
- Childhood Asthma Control Test
- Tape Stripping (Biomarker Assessment)
- Observer Reported Itch Assessment (ORIA; ages 3 months - ≤ 11 years)
- Patient Reported Itch Severity Scale (ages 6 years to ≤ 11 years old)
- Observer Global Impression of Severity (OGIS; ages 3 months - ≤ 11 years)
- Peak Pruritis NRS (Caregivers)
- Children's Sleep Health Questionnaire (CSHQ; ages ≥4-≤ 11) OR Brief Infant Sleep Questionnaire(BISQ; ages 3 months-<4 years)
- Medical Outcome Sleep Scale (MOS; caregivers only)
- Mobile Device Proficiency Questionnaire (MDPQ; caregivers only)
- Faces, Legs, Activity, Cry, and Consolability Scale (FLACCS)
- Dermatitis Family Impact Questionnaire (DFI; parent/guardian(s); ages 3 months- ≤ 11 years)
- Children's Dermatology Life Quality Index (CDLQI; ages ≥4-≤ 11 years) OR Infants Dermatitis Quality Of Life Index (IDQOL; ages 3 months-<4 years)
- Observer-reported Patient-Oriented Eczema Measure (POEM); ages 3 months – ≤ 11 years)
- The participant will be asked to don the accelerometry/actigraphy devices (coordinator will log dispensing) as follows: The participant will be provided the accelerometry/actigraphy devices immediately after completion of informed consent and will be trained. Devices will be optional for child participants who have active AD on location of device placement, with a minimum of at least one wrist device needed for enrollment.
 - Accelerometry
 - Children: Ages 2 years to ≤ 11 years; On R & L wrists
 - Caregivers: Ages 18 to 75 years; On R & L wrists
 - Actigraphy or accelerometry:
 - (Ages 3 months up to ≤ 11 years; On R & L wrists and R & L ankles for 3 months - <2 years; R & L wrists only for 2 – ≤ 11 years)

Out-of-Laboratory (At-Home) Assessments (Days -7–Day 1; Between Visits 1 & 2):

The purpose of the out-of-laboratory assessment is to evaluate wearable devices in a home/routine setting (defined as the participant's routine environment/activities). Participants will be provided a fully-charged set of accelerometry devices for use at home. Devices will be optional for child participants who have active AD on location of device placement, with a minimum of at least one wrist device needed for enrollment.

1. Continuously wear Accelerometry devices as much as possible

2. Continuously wear Actigraphy devices as much as possible

Visit 2 (V02)/ Day 1 (+/- 3 days)- In Laboratory (~1 hour):

